Specific Aim 2: To examine the moderating effects of MCI on intervention efficacy. We will also test for moderation effects to determine at what stage along the cognitive status continuum—without MCI vs. MCI—intervention is most effective. To do so, we will examine three-way interactions (MCI x training group x time) for the CAP, cognitive, and everyday function composites. When an interaction is significant, we will stratify analyses by MCI status and examine effect sizes. Effect sizes from pre- to post- training relative to controls will be compared for participants with/without MCI. An alpha of .05 will be used for these analyses.

Participants who score 26 or higher on the MoCA will be defined as no MCI (i.e., cognitively normal). Those participants who score a 20-25 on the MoCA will be defined as MCI if they score a 0.5 on the CDR and have performance at or 1 SD below their age, sex, and education norms on any of the following measures: Trails, Verbal Fluency, Digit Coding, Craft Story Recall, Multilingual Naming Test, or Benson Complex Figure. Those with MoCA scores 20-25 who score 0 on the CDR, but have performance at or 1SD below expected for age, sex, and education will be adjudicated prior to analyses. If an individual scores 20-25 on the MoCA, and 0.5 on the CDR, but has performance above expected on all of the aforementioned measures, their case will be adjudicated prior to analyses. The study physicians will adjudicate such cases prior to coding of MCI status for final analyses.

To quantify the effects of piano training further, in addition to examining composite outcomes as detailed above, we will calculate and report effect sizes for pre-to-post change of piano training relative to controls for each individual measure of CAP, cognition, and everyday function for the sample overall as well as stratified by MCI status and among those who were adherent only (80% or more of sessions completed).

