Hearing	-0.09	0.06	.134	-0.14	0.06	.016
Visual acuity	-6.55	5.33	.220	-15.45	5.12	.003
Expectations	-0.79	0.67	.234	-1.96	0.64	.003
	Timed IADL+			Test of Everyday Attention		
Intercept	48.89	1.32	<.001	62.34	1.15	<.001

Group	3.15	2.67	.240	1.37	2.33	.557
Time	0.14	0.79	.863	-8.61	0.67	<.001
Group x time	-1.53	1.58	.327	-0.40	1.340	.765
Hearing	0.07	0.57	.194	-0.02	0.05	.603
Visual acuity	12.75	4.770	.008	0.24	4.470	.957
Expectations	1.02	0.59	.089	-0.79	0.56	.157

Note. ATTR=Adaptive Tests of Temporal Resolution, IADL=instrumental activities of daily living. MCI=mild cognitive impairment. +For ATTR and Timed IADL lower scores reflect better performance.

Table 14.3. *Effect sizes for piano training relative to music listening across composite outcomes and assessments for the analytic sample overall, among those adherent, and by cognitive status.*

Outcome Measure	d Effect Size			
	Overall (n =198)	Adherent (n =189)	Non-MCI (n =146)	MCI (n =52)
Central auditory processing composite	-0.01	-0.01	0.00	-0.07
Dichotic Digits	-0.06	-0.07	-0.03	-0.14
Dichotic Sentence Identification	0.01	0.01	0.02	-0.07
Time Compressed Speech	-0.01	0.01	0.03	-0.06
Words in noise	0.03	0.03	0.12	0.01
Adaptive Tests of Temporal Resolution composite	0.17	0.20	-0.09	0.24
Cognitive composite	-0.03	-0.03	-0.10	0.08
Trails A	0.03	0.06	0.00	0.43
Trails B	-0.17	-0.20	0.01	-0.54
Digit Symbol Coding	0.08	0.09	0.06	0.26
Test of Everyday Attention - Visual elevator timing subtest	0.02	0.02	0.03	0.44
Test of Everyday Attention - Telephone search time	-0.29	-0.32	0.08	-0.27
Verbal fluency composite	0.05	0.06	0.09	-0.12

Letter fluency	0.00	0.02	0.09	-0.36
Category fluency	0.18	0.20	0.18	0.13
Switching fluency	-0.06	-0.05	-0.07	-0.05
Test of Everyday Attention composite	0.04	0.08	-0.30	-0.02
Visual Elevator accuracy	0.01	0.03	-0.12	-0.19
Dual task decrement	0.10	0.13	-0.18	0.22
Timed Instrumental Activities of Daily Living composite	-0.15	-0.21	0.09	-0.13

Note. MCI=mild cognitive impairment. *d* effect sizes were calculated as pre- to post- change in the piano training condition relative to the music listening condition divided by the baseline standard deviation such that positive values would indicate improvement. Adherent analyses include those who completed 15 or more sessions of the assigned condition.

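### Several rows of Table 14.3 do not reconcile under its stated definition of d: the overall effect sizes do not follow from the non-MCI and MCI values

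*Combined protocol and SAP*

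**What the plan says.** Section 9.6 tests Aim 2 by the three-way interaction of MCI, group and time. If that is significant, "Effect sizes from pre- to post- training relative to controls will be compared for participants with/without MCI". The same section separately plans descriptive effect sizes for every measure, overall and by MCI status.

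Table 14.3 in Section 14 (Results) reports them in four columns: overall (n=198), adherent (n=189), non-MCI (n=146) and MCI (n=52). Its note says that "effect sizes were calculated as pre- to post- change in the piano training condition relative to the music listening condition divided by the baseline"; the divisor is thus an SD at baseline, and positive values mean improvement. It does not say whether that SD belongs to the whole sample, the subgroup or the arm.

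The rows at issue include "Telephone search time -0.29 -0.32 0.08 -0.27", "Test of Everyday Attention composite 0.04 0.08 -0.30 -0.02", "Timed Instrumental Activities of Daily Living composite -0.15 -0.21 0.09 -0.13", "Visual Elevator accuracy 0.01 0.03 -0.12 -0.19", "Adaptive Tests of Temporal Resolution composite 0.17 0.20 -0.09 0.24" and "Dual task decrement 0.10 0.13 -0.18 0.22".

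The Section 14 text reports no significant three-way interaction (all p above .245) and no evident improvement in those without MCI. It reports potential small benefits (d of at least 0.25) in those with MCI on Trails A, Digit Symbol Coding and one TEA subtest.

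**The concern.** The two cognitive-status groups partition the analysed sample. With one SD per measure and similar MCI shares in the two arms, the overall difference in change must be the weighted average of the two subgroup differences, and so must lie between them. Several rows break this, some with a change of sign.

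At stake is the descriptive evidence on who might benefit. The only favourable statement about piano training in Section 14 rests on the MCI column of this table.

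**Working it through.** **Inputs.** The d values and n come from Table 14.3, group-by-time and time estimates from Table 14.2, and sex counts by arm and cognitive status from Table 14.1.

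**1. The overall column against Table 14.2.** Intercepts of 46 to 62 suggest T-scaling. Assume SD 10 and group coded music minus piano; neither is stated. Then d = -(group x time)/10, with the sign reversed for ATTR and Timed IADL, where lower is better.

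| Outcome | Group x time | Implied d | Printed overall d |
|---|---|---|---|
| ATTR | 1.51 | 0.15 | 0.17 |
| CAP | 0.465 | -0.05 | -0.01 |
| Verbal fluency | -0.29 | 0.03 | 0.05 |
| Cognition | 0.39 | -0.04 | -0.03 |
| Timed IADL | -1.53 | -0.15 | -0.15 |
| TEA | -0.40 | 0.04 | 0.04 |

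The overall column agrees with the model within 0.04.

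**2. Weighted average of the subgroups.** d_w = (146 x d_nonMCI + 52 x d_MCI)/198, with weights 0.737 and 0.263. For the TEA composite: (146 x -0.30 + 52 x -0.02)/198 = -44.84/198 = -0.226.

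| Row | Overall | Non-MCI | MCI | d_w | Overall - d_w |
|---|---|---|---|---|---|
| Telephone Search | -0.29 | 0.08 | -0.27 | -0.012 | -0.278 |
| Timed IADL | -0.15 | 0.09 | -0.13 | 0.032 | -0.182 |
| TEA composite | 0.04 | -0.30 | -0.02 | -0.226 | 0.266 |
| Visual Elevator accuracy | 0.01 | -0.12 | -0.19 | -0.138 | 0.148 |
| ATTR | 0.17 | -0.09 | 0.24 | -0.003 | 0.173 |
| Dual task decrement | 0.10 | -0.18 | 0.22 | -0.075 | 0.175 |
| Visual Elevator timing | 0.02 | 0.03 | 0.44 | 0.138 | -0.118 |
| Trails A | 0.03 | 0.00 | 0.43 | 0.113 | -0.083 |
| Words in noise | 0.03 | 0.12 | 0.01 | 0.091 | -0.061 |

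In the first four rows the overall d lies outside both subgroup values beyond rounding of 0.005. Visual Elevator timing is also outside, but within rounding. In the other 11 of the 20 rows d_w is within 0.04 of the printed value.

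**3. Could subgroup-specific SDs explain it?** Let s_n and s_m be the subgroup SDs divided by the overall SD. Then d_overall = 0.737 d_n s_n + 0.263 d_m s_m, with 0.737 s_n² + 0.263 s_m² no greater than 1.
- TEA composite and Visual Elevator accuracy: both subgroup values are negative, so no SDs give a positive overall value.
- Where only the MCI value has the right sign, the furthest reachable value is d_m x √(52/198) = 0.5125 d_m. Allowing for rounding: Telephone Search -0.275 x 0.5125 = -0.14 (printed -0.29); Timed IADL -0.135 x 0.5125 = -0.07 (printed -0.15); ATTR 0.245 x 0.5125 = 0.13 (printed 0.17). None is reachable.
- Dual task: 0.225 x 0.5125 = 0.115, so 0.10 is reachable, but only with a non-MCI SD near zero.
- Trails A and Visual Elevator timing need an MCI SD of at most about 0.35 and 0.22 of the overall SD.

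**4. Could a different n per row explain it?** Reweighting two values cannot leave the interval between them, so this alone cannot rescue the first four rows. ATTR would need an MCI weight of (0.17 + 0.09)/0.33 = 0.79, and dual task (0.10 + 0.18)/0.40 = 0.70, against 0.26.

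**5. Could unequal MCI shares by arm explain it?** The sex counts in Table 14.1, with percentages read as truncated, fit 96 non-MCI and 37 MCI for piano (63/96 = 65.6%, 18/37 = 48.6%) and 97 and 38 for music (58/97 = 59.8%, 17/38 = 44.7%). The total is 268, matching F(1,266). MCI shares at randomisation are then 37/133 = 27.8% and 38/135 = 28.1%. Suppose, assuming 99 analysed per arm, that the 52 split 30/22. Let g be the MCI minus non-MCI mean change in the music arm. For Timed IADL, 0.09 - 0.22 x 30/99 + (8/99) g = -0.15, so g = -2.1 SD; the reverse split gives 2.4 SD. Telephone Search needs 3.3 to 3.6 SD and the TEA composite 3.2 to 3.4 SD. A 30/22 split would itself mean retention of 30/37 = 81% against 22/38 = 58%.

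**6. A check inside one column.** Section 14 builds composites by averaging z scores. The five components listed under the non-MCI cognitive composite are 0.00, 0.01, 0.06, 0.03 and 0.08 (mean 0.18/5 = 0.036), yet the composite is -0.10. In the other columns the signs agree: overall mean -0.33/5 = -0.066 against -0.03; MCI 0.32/5 = 0.064 against 0.08. This check does not depend on MCI shares; it assumes the same participants and one SD per measure.

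**7. A sign error?** Reversing only the non-MCI sign brings ATTR to 0.129 (printed 0.17) and Timed IADL to -0.101 (printed -0.15), but Telephone Search only to -0.130 (printed -0.29). Inconsistent reversal may contribute but does not explain every row.

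**The case against.** A reader might infer that these rows are arithmetically impossible. The documents do not support that, because the note leaves the SD undefined, and neither per-row n nor the MCI-by-arm split of the 198 is given. Arm-specific SDs are a real alternative for the TEA composite. It falls by 8.61 points, about 0.86 SD if T-scaled, so a music-arm SD 15% to 25% below the piano-arm SD shifts d by 0.86 x (1/0.85 - 1) = 0.15 to 0.86 x (1/0.75 - 1) = 0.29 with no treatment difference. That stands for TEA. It gives Timed IADL little help: its time effect is 0.14 points, about 0.01 SD.

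A reader might also infer that all the subgroup effect sizes, or the Aim 2 conclusion, are discredited. Neither follows. Eleven of 20 rows reconcile, including Digit Symbol Coding (0.113 against 0.08), and Aim 2 was tested by interactions that do not use these values.

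Nor must the Section 14 sentences be wrong. Holding the MCI values fixed, the non-MCI d needed to reproduce the overall column is -0.30 for Telephone Search, -0.16 for Timed IADL, 0.06 for TEA, 0.08 for Visual Elevator accuracy, 0.15 for ATTR and 0.06 for dual task. None reaches 0.25, so the statement of no evident improvement without MCI would survive.

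Finally, the agreement with Table 14.2 rests on an assumed SD and a group coding inferred from fit. It is supporting evidence, not proof.

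**Conclusion.** The point holds as a failure to reconcile under the stated definition. Four rows have an overall d outside both subgroup values, with gaps from the weighted average of 0.15 to 0.28. ATTR and dual task miss it by about 0.17 each; ATTR cannot be reached with any subgroup SDs, and dual task only with an extreme one. Trails A and Visual Elevator timing, two of the three rows behind the MCI-benefit sentence, miss by 0.08 and 0.12 and need implausible SDs. The non-MCI cognitive composite contradicts its own components.

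The subgroup columns are the likely source. This rests on near-equal MCI shares by arm (supported by Table 14.1), the same participants across columns within a row, and no arm-specific SDs. Timed IADL is firmer evidence than the TEA composite. The affected values are descriptive; the non-significant three-way interactions stand.

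**What to change.** Recompute Table 14.3 with one sign rule and one stated SD, the overall baseline SD of each measure, in all columns. Give the n for each row and the MCI-by-arm counts. Before release, check that the weighted subgroup values reproduce the overall column and that each composite agrees with its components. State the group coding and score scale in Table 14.2. Then recheck the descriptive subgroup sentences in Section 14, above all those on Trails A and the TEA subtest in MCI, and revise them only if the corrected values require it. If arm- or subgroup-specific SDs were intended, say so in the note. The cost is re-running one table on existing data.
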